10.2.3 Pregnancy reporting

If a female trial participant becomes pregnant, the pregnancy consent form should be presented to the trial participant. The participant must be given adequate time to read, review and sign the pregnancy consent form. This consent form is necessary to allow the investigator to collect and report information regarding the pregnancy. To ensure participant safety, each pregnancy occurring after signing the informed consent must be reported to Novartis within 24 hours of learning of its occurrence. The pregnancy should be followed up to determine outcome, including spontaneous or voluntary termination, details of the birth, and the presence or absence of any birth defects, congenital abnormalities, or maternal and/or newborn complications. Risks to the fetus of recombinant AAV gene therapy to the fetus are unknown. Since there is a difference in risks between the treatment groups, all pregnancy cases must be unblinded. The investigator will break the study blind for that participant and inform the participant which treatment she was on. This applies also when pregnancy occurs in partners of male participants.

Pregnancy should be recorded and reported by the investigator to the Novartis Chief Medical Office and Patient Safety (CMO&PS). Pregnancy follow-up should be recorded on the same form and should include an assessment of the possible relationship of OAV101 to any pregnancy outcome. Any SAE experienced during pregnancy must be reported.

If a female partner of a male trial participant who took study treatment in this study becomes pregnant, pregnancy outcomes should be collected. Consent to report information regarding these pregnancy outcomes should be obtained from the mother.

After consent is provided, the pregnancy reporting will occur up to one year after the estimated date of delivery.

NOTE: Payment for all aspects of obstetrical care, child or related care will be the participant's responsibility.

10.2.4 Reporting of study treatment errors including misuse/abuse

Medication errors are unintentional errors in the prescribing, dispensing, administration or monitoring of a medicine while under the control of a healthcare professional, participant or consumer (EMA definition).

- Misuse refers to situations where the medicinal product is intentionally and inappropriately used not in accordance with the protocol
- Abuse corresponds to the persistent or sporadic, intentional excessive use of a medicinal product, which is accompanied by harmful physical or psychological effects.

Study treatment errors and uses outside of what is foreseen in the protocol will be recorded on the appropriate CRF irrespective of whether or not associated with an AE/SAE. Study treatment errors and uses outside of what is foreseen in the protocol, misuse or abuse will be collected and reported in the safety database irrespective of it being associated with an AE/SAE within 24 hours of Investigator's awareness. For more information on AE and SAE definition and reporting requirements, please see the respective sections.

10.3 Additional Safety Monitoring

10.3.1 Liver safety monitoring

To ensure participant safety and enhance reliability in determining the hepatotoxic potential of OAV101, a standardized process for identification, monitoring and evaluation of liver events has to be followed.

Please refer to [Appendix 2, Section 16.2.1](#) for complete definitions of liver laboratory triggers.

Once a participant is exposed to study treatment, every hepatotoxicity event defined in [Section 16.2.1](#) should be followed up by the Investigator or designated personnel at the trial site, as summarized below. Additional details on actions required in case of liver events are outlined in [Table 16-1](#) and [Table 16-2](#).

If elevated, repeat liver chemistry tests (i.e., ALT, AST, TBL, PT/INR, ALP, and G-GT) will be performed within 48-72 hours to confirm elevation. These liver chemistry repeats should be performed. At a local laboratory to monitor the safety of the participant. Any local liver chemistry tests should have results recorded on the appropriate CRF.

If the initial elevation is confirmed, follow-up requirements will be performed based on the liver laboratory trigger, and per [Table 16-1](#) and [Table 16-2](#):

[figure not shown]
[figure not shown]
[figure not shown]
[figure not shown]
[figure not shown]
[figure not shown]
[figure not shown]
[figure not shown]
[figure not shown]
- Hospitalization of the participant, if appropriate
- Causality assessment of the liver event
- Thorough investigation and follow-up of the liver event, which may include:
 - Based on Investigator's discretion: serology tests, laboratory tests for other causes of hepatitis, including viral hepatitis, imaging such as abdominal ultrasound/Fibroscan (i.e., elastography), and pathology assessments
 - Obtaining a more detailed history of signs and symptoms and prior or concurrent diseases

- Obtaining a history of concomitant drug use, including nonprescription medications (e.g., acetaminophen); and herbal and dietary supplement preparations
- Exclusion of underlying liver disease
- Pediatric gastroenterology or hepatology consultations, if appropriate

All follow-up information and procedures performed must be recorded as appropriate in the CRF.

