16.2.3 Follow up requirements for liver laboratory triggers - isolated hyperbilirubinemia

Table 16-2 Follow-up requirements for liver laboratory triggers - isolated hyperbilirubinemia

Criteria Total Bilirubin (isolated)	Actions required	Follow-up monitoring
>1.5 – 3.0 x ULN	
 Repeat LFTs within 48-72 hours 	
 Monitor LFTs weekly until resolution to ≤ Grade 1 or to baseline
> 3 – 10 x ULN (in the absence of known Gilbert's syndrome)	
 Repeat LFTs within 48-72 hours Hospitalize if clinically appropriate Establish causality Record the AE and contributing factors (e.g. concomitant medications, medical history, labs) in the appropriate CRF 	
 Monitor LFTs weekly until resolution to ≤ Grade 1 or to baseline (ALT, AST, TBL, Alb, PT/INR) Test for hemolysis (e.g. reticulocytes, haptoglobin, unconjugated [indirect] bilirubin)
> 10 x ULN	
 Hospitalize the participant Establish causality Record the AE and contributing factors (e.g. concomitant medications, medical history, laboratory evaluations) in the appropriate CRF 	
 ALT, AST, TBL, Alb, PT/INR, until resolution (frequency at investigator discretion)

LFT(s) = liver function test
Based on investigator's discretion, investigation(s) for contributing factors for the liver event can include: Serology tests, imaging and pathology assessments, pediatric gastroenterologist's or hepatologist's consultancy; obtaining more detailed history of symptoms and prior or concurrent diseases, history of concomitant drug use, exclusion of underlying liver disease.

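### Section 10.3.1 makes liver follow-up wait for a confirming repeat test, which contradicts the mandatory hospitalization in Table 16-2 at total bilirubin above 10x ULN

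*Protocol*

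**What the plan says.** Protocol section 10.3.1 presents itself as the standard process that sites must follow for liver events, and section 8.4.1.4 sends sites there for aminotransferase rises after dosing. Its scope is every trigger in section 16.2.1: "Once a participant is exposed to study treatment, every hepatotoxicity event defined in" that section is to be followed up. The steps are then given in order:

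- For an elevated value, "repeat liver chemistry tests (i.e., ALT, AST, TBL, PT/INR, ALP, and G-GT) will be performed within 48-72 hours to confirm elevation".
- Then: "If the initial elevation is confirmed, follow-up requirements will be performed based on the liver laboratory trigger", with reference to Tables 16-1 and 16-2.
- The list that follows this condition begins with "Hospitalization of the participant, if appropriate", then causality assessment and investigation.

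The same section also says "Additional details on actions required in case of liver events are outlined in" the two tables.

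The tables start from the laboratory value and do not mention confirmation. In Table 16-2 (section 16.2.3), the row for isolated TBL above 10x ULN says "Hospitalize the participant" and lists no repeat. The row for TBL >3-10x ULN lists "Repeat LFTs within 48-72 hours" and then "Hospitalize if clinically appropriate". In Table 16-1 (section 16.2.2), the ALT >5x ULN row lists a repeat panel within the same window together with close monitoring, discretionary hospitalization and a work-up for other causes.

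**The concern.** Hepatotoxicity is the first risk listed for OAV101 in section 4.5.3. Read literally, 10.3.1 has a site wait for a second blood test before it applies the tables, whatever the first value was. For bilirubin above 10x ULN the table orders admission. A site working from 10.3.1 could therefore hold back an admission that a site working from the table would arrange at once. The readable text of 10.3.1 makes no exception for severe values. At stake are prompt care in a severe liver event and uniform handling across sites. The efficacy analysis is not affected.

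**Working it through.** The check compares texts. The only arithmetic is a row count and a count of exposed children.

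**Inputs.** Section 10.3.1 for the order of steps; Table 16-1 (4 rows) and Table 16-2 (3 rows) for the actions; sections 6.7.2, 10.2.2, 14.1 and 16.2.4 for anything that overrides or bypasses the order.

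**Row by row.**

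| Row | Repeat listed in the table? | Hospitalization in the table | Against 10.3.1 |
|---|---|---|---|
| 16-2: TBL >10x ULN | No | Required | Contradiction |
| 16-2: TBL >3-10x ULN | Yes | Discretionary | Ambiguous order |
| 16-1: ALT >5x ULN | Yes | Discretionary | Ambiguous order |
| 16-1: ALT or AST >3x ULN with TBL >2x ULN or INR >1.5 | Only if blank cell is merged | Discretionary, if merged | Ambiguous order |
| 16-1: ALT >3x ULN with symptoms | Only if blank cell is merged | Discretionary, if merged | Ambiguous order |
| 16-1: ALT >3x ULN, normal TBL, no symptoms | Yes | None | No material conflict |
| 16-2: TBL >1.5-3.0x ULN | Yes | None | No material conflict |

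Count: 1 + 4 + 2 = 7 rows, which matches 4 + 3.

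**The contradicted row.** 10.3.1 differs from Table 16-2 in two ways. It places hospitalization after confirmation, and it makes hospitalization discretionary. The table does neither.

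**The four ambiguous rows.** Here the 48-72 hour repeat is both the precondition in 10.3.1 and an action inside the table. The tables state no order among their actions. If they began only after confirmation, their own repeat would be a second one. The panels also differ: the severe-row panel in Table 16-1 includes fractionated bilirubin, albumin, CK and GLDH, which the 10.3.1 panel does not name. This suggests that the tables were meant to start at the first value, but no text says so.

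**Other routes to the tables.** The readable part of section 16.2.4 refers cases meeting 16.2.1 to Tables 16-1 and 16-2 without a confirmation step; the start of that sentence is redacted. Section 10.2.2 requires close follow-up of a potential Hy's Law case, with no confirmation step and no stated start time.

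**Length of delay.** The upper end of the repeat window is 72 hours, or 72 / 24 = 3 days. The lower end is zero if the investigator acts on the first value.

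**Children exposed.** About 75 receive OAV101 in Period 1. Of about 50 sham participants, the protocol expects at most 5 to be barred by antibodies, so up to 50 - 5 = 45 to 50 follow in Period 2. The total is up to 75 + 45 = 120 to 75 + 50 = 125, before dropout and other Period 2 exclusions. The documents give no expected frequency of severe liver values, so no number of affected children can be derived.

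**The case against.** The strongest reply is that 10.3.1 describes itself as a summary and points to the tables for detail, so the tables should govern and can be read as acting on the first value. Sections 16.2.1 and 16.2.4 support this, since their readable text leads to follow-up without a confirmation step. The 48-72 hour window is an outer limit, and the repeat is done at a local laboratory. Nothing in 10.3.1 forbids earlier action. Section 6.7.2 leaves treatment of adverse events to medical judgement, and section 14.1 expects immediate safety action even where it departs from the protocol. Confirming a value before a work-up is also ordinary practice, because it spares children tests for a spurious result.

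Most of this stands, and it makes harm unlikely where clinicians use judgement. It does not reconcile the TBL >10x ULN row with 10.3.1. Nor should admission of a child with such a value depend on a clause that excuses deviations.

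Two stronger readings are tempting. A reader might infer that 10.3.1 contradicts all five severe rows. The documents do not support that: four of them list the repeat among their own actions, state no order, and leave hospitalization to judgement. A reader might also infer that the confirmation step delays Hy's Law reporting or care. It does not delay reporting, because 10.3.1 governs follow-up and not SAE reporting. On care, section 10.2.2 is a separate duty without a confirmation step, so it reduces the concern.

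**Conclusion.** The concern holds in a narrow form. One of seven rows, isolated TBL above 10x ULN, is directly contradicted by 10.3.1. In four other severe rows the order of actions is unclear, two of them only if the blank action cells in Table 16-1 are read as merged with the ALT >5x ULN cell. The two mild rows need no change. The possible delay runs from zero to 72 hours and arises only on a literal reading of 10.3.1.

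The conclusion has limits. Nine figures directly after the conditional sentence in 10.3.1 are not shown in the text reviewed, and parts of 10.3.2 and 16.2.4 are redacted, so clarifying wording may exist there. The fatal acute liver failures reported in section 4.5.3 stand under the intravenous overview, and the intrathecal liver data are redacted. A reader should therefore not infer a fatality risk for this trial from them. The point is a wording defect in a safety procedure that is worth correcting; it is not evidence that participants have been or will be harmed.

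**What to change.** Add to section 10.3.1: *Hospitalization for TBL >10x ULN does not await confirmation. For the other severe rows of Tables 16-1 and 16-2 and for potential Hy's Law cases, the repeat test runs in parallel with, and does not delay, clinically needed monitoring, work-up or hospitalization.*

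Keep confirmation first for the two mild rows (asymptomatic ALT >3x ULN with normal TBL; TBL >1.5-3.0x ULN), and keep the Gilbert's syndrome qualifiers in the tables. If the blank cells in Table 16-1 are not merged in the source document, fill them in.

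The cost is a protocol amendment and a letter to sites. The clinical cost is an occasional admission or work-up for a value that proves transient or erroneous. That work-up may mean extra blood tests for a child, since footnote a of Table 16-1 allows viral hepatitis, other viral and autoimmune panels. The words *clinically needed* keep that decision with the investigator.

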10.3.2 CCI

CCI

[figure not shown][figure not shown]
Refer to [Section 8.3.1](#) for details pertaining to the completion of assessments.

Testing Procedure

[CCI](#)

Figure 12-1

12.5.2 Safety endpoints

For all safety analyses, the Safety Set will be used. All listings and tables will be presented by treatment group.

Safety summaries (tables, figures) will include only data from the post-treatment period with the exception of baseline data, which will also be summarized where appropriate (e.g., change from baseline summaries). In addition, a separate summary for deaths occurring post-treatment will be provided. In particular, summary tables for adverse events (AEs) will summarize only on-treatment events, with a start date on or after the date of dose administration (treatmentemergent AEs).

The on-treatment period lasts from the date of administration of study treatment to completion of the study at Week 64.

Adverse events

All information obtained on adverse events will be listed by treatment group and participant.

The number (and percentage) of participants with treatment emergent adverse events (events with an onset after the dose of study medication or events which were present prior to start of double-blind treatment but increased in severity, changed from being not suspected to being suspected of study drug relationship, or developed into SAEs after the start of the treatment period) will be summarized in the following ways:

- by treatment group, primary system organ class and preferred term.
- by treatment group, primary system organ class, preferred term and maximum severity.

- by treatment group, Standardized MedDRA Query (SMQ) and preferred term.

Separate summaries will be provided for study medication related adverse events, deaths, serious adverse events, and other significant adverse events leading to discontinuation.

The number (and proportion) of participants with AESIs will be summarized by treatment.

A participant with multiple adverse events within a primary system organ class is only counted once towards the total of the primary system organ class.

Vital signs

All vital signs data will be summarized by treatment and visit/time.

12-lead ECG

All ECG data will be summarized by treatment and visit/time.

PR, QRS, QT, QTcF, and RR intervals will be obtained from 12-lead ECGs for each participant during the study.

Categorical analysis of QT/QTc interval data based on the number of participants meeting or exceeding predefined limits in terms of absolute QT/QTc intervals or changes from Baseline will be presented.

Echocardiogram

All echocardiogram data will be summarized by treatment and visit/time. Additionally, the following will be summarized:

- Number and percentage of participants with intracardiac thrombi
- Number and percentage of participants with low cardiac function

These parameters are defined as follows:

Intracardiac thrombi: Post-baseline ECHO result of thrombus present (response of Yes)

Low cardiac function: Post-baseline ECHO results of LVEF < 56% or LVFS < 28%

Clinical laboratory evaluations

All laboratory data will be summarized by treatment and visit/time. Shift tables using the low/normal/high classification as well as CTCAE grades will be used to compare baseline to the worst on-treatment value.

CCI

CCI

12.6 Analysis of exploratory endpoints

The exploratory objectives are described in [Table 2-1](#).

The full list of exploratory endpoints to be included in the CSR and detailed analysis methods will be detailed in the study SAP.

12.6.1 CCI

CCI

Additional data, from other clinical trials, are often needed to confirm associations. Alternatively, if the number of participants enrolled in the study is too small to complete proper statistical analyses, the data may be combined, as appropriate, with those from other studies to enlarge the dataset for analysis.

Data generated on hypothesis-free platforms will be reported separately (e.g., CSR addendum).

12.6.2 CCI

CCI [REDACTED], will be tabulated with descriptive statistics by visit and treatment. Additional exploratory analyses and their results, if applicable, will be included CCI [REDACTED]

12.6.3 CCI

CCI

CCI

12.7 Interim analyses

No formal interim analysis is planned for this trial.

12.8 Sample size calculation

The sample size calculation is primarily based on the primary variable, change from Baseline in HFMSE total score.

12.8.1 CCI

CCI

Assuming a true treatment difference in the change from Baseline in HFMSE of 3 points and a standard deviation of 5 points, a sample size of 125 participants (75 in the OAV101 treatment group and 50 in the sham procedure group) provides approximately 90% power that the primary analysis will be statistically significant at the two-sided 5% alpha level assuming a minimal number of participants prematurely withdraw from the study prior to Week 52. In addition, assuming a larger treatment difference in the change from Baseline in HFMSE total score of 5 points and the same standard deviation as anticipated in the overall study population (5 points) in the ≥ 2 to < 5 years old group, a sample size of 65 participants (39 in the OAV101 treatment group and 26 in the sham procedure group) could achieve $> 95\%$ power in this younger age group.

12.8.2 Secondary endpoint(s)

Sample size considerations were primarily based on the primary endpoint.

Because this is the first OAV101 clinical trial to include the RULM assessment, there are no historical data available upon which to base sample size calculations on.

In the AVXS-101-CL-102-IT clinical trial, the HFMSE responder endpoint was defined as the achievement of improvement in HFMSE of ≥ 3 points at any post baseline time point (through Month 12): 11/12 (91.7%) patients treated with OAV101 achieved response, compared to 2/15 (13.3%) patients in the PNCR group. For the current study, the responder endpoint is defined as the achievement of improvement in HFMSE of ≥ 3 points at the end of follow-up period 1 (and will be based on the average of the HFMSE scores at Month 11 and Month 12). Applying this same definition to the AVXS-101-CL-102-IT data, 9/12 (75%) patients treated with OAV101 achieved response. For PNCR, HFMSE was assessed less frequently (the last 2 time points of relevance were Month 9 and Month 12). Considering just the PNCR patients with HFMSE data at Month 9 and/or Month 12, then based on the average of these 2 scores or based on the single available score, 2/15 (13%) achieved response. The power to detect a significant difference in the ≥ 2 to < 5 year age group in this study, assuming a response rate of 75% for OAV101 and 13% for sham and alpha=0.05, would be $> 99\%$ with the planned sample size of N=65 patients (39 in OAV101, 26 in sham).

13 Ethical considerations and administrative procedures

13.1 Regulatory and ethical compliance

This clinical study was designed and shall be implemented, executed and reported in accordance with the ICH Harmonized Tripartite Guidelines for Good Clinical Practice, with applicable local regulations (including European Directive 2001/20/EC, US CFR 21), and with the ethical principles laid down in the Declaration of Helsinki.

13.2 Responsibilities of the investigator and IRB/IEC

Before initiating a trial, the investigator/institution must obtain approval/favorable opinion from the Institutional Review Board/Independent Ethics Committee (IRB/IEC) for the trial protocol, written informed consent form, consent form updates, participant recruitment procedures (e.g., advertisements) and any other written information to be provided to participants. Prior to study start, the investigator is required to sign a protocol signature page confirming his/her agreement to conduct the study in accordance with these documents and all of the instructions and procedures found in this protocol and to give access to all relevant data and records to Novartis monitors, auditors, Novartis Quality Assurance representatives, designated agents of Novartis, IRBs/IECs, and regulatory authorities as required. If an inspection of the clinical site is requested by a regulatory authority, the investigator must inform Novartis immediately that this request has been made.

13.3 Publication of study protocol and results

The protocol will be registered in a publicly accessible database such as clinicaltrials.gov and as required in EudraCT. In addition, after study completion (defined as last participant last visit) and finalization of the study report the results of this trial will be submitted for publication and posted in a publicly accessible database of clinical trial results, such as the Novartis clinical trial results website and all required Health Authority websites (e.g., Clinicaltrials.gov, EudraCT etc.).

For details on the Novartis publication policy including authorship criteria, please refer to the Novartis publication policy training materials that were provided to you at the trial Investigator meetings.

Any data analysis carried out independently by the Investigator should be submitted to Novartis before publication or presentation.

Summary results of primary and secondary endpoints will be disclosed based upon global Last Participant Last Visit (LPLV) date, since multinational studies are locked and reported based upon the global LPLV.

